If randomized to the intervention arm, a binder containing the intervention study material will be sent to the participant's home address. The study binder will include a manual to serve as a guide for the patient to follow during each tele-delivered session with the health coach and activity tracker to document step counts and impact on pain and depression. Appointment reminders will be mailed prior to each intervention session. Depending on the content of the session, these reminders may also include a list of the participant's values, goals, and action plan as discussed during prior sessions. Additional session reminders will be delivered via telephone in addition to mailed appointment reminders.

A research team member, not the health coach, will call each participant for outcome assessments at baseline, mid-intervention and post-intervention, regardless of intervention arm assignment. These data

will be collected using UTSW REDCap, a secure web application that can be used to distribute and manage online survey tools and databases. Upon study completion, semi-structured interviews will elicit stakeholder and participant perceptions of health coach recommendations and use of action plans (see **Table 1** for key informant interview topics).

Database Management

[figure not shown]
The UTSW Redcap has been programmed with the specific outcomes assessments for this project, and we will use Redcap to document all electronic data management activities including tracking of screening, recruitment, and progress through the intervention and assessments. The study data will be stored on the UTSW network or on the REDCap survey website. The data from health coaching telesessions (i.e. goals set by participants, achievement of goals, barriers to achieving desired goals) will be entered into a parallel health coaching manual (word document) that will be IRB approved and stored behind the UTSW firewall in the study secure research folder.

Study data will be stored within password protected data management programs, on password protected computers. Only IRB approved study personnel will have access to study data. All research staff will be trained in the appropriate safeguarding of confidential data and in the protection of human participants. At the end of the study, after analyses are complete, all study data will be de-identified, and the identifying key will be destroyed per UTSW and Parkland policies and regulations. The health coach will have restricted access to the study database; he/she will also have access to EMR as needed.

Outcome Assessments and Data Collection

Using age >50, ICD-10 codes for chronic back pain and depression as criteria, an initial data pull from patients' EMR will yield a list of potentially eligible prospective study participants. The research team will pre-screen this list of potentially eligible patients for recruitment. As outlined in section **Recruitment Strategy and Informed Consent Process**, participant recruitment may occur in-person or by tele-based method and will include an introduction to the study and **verbal consent**. Upon completion of consent, a research staff member will further screen for eligibility and arrange a separate telephone call for a baseline assessment. As seen in the **Figure 2** below, a research team member, not the health coach, will complete all outcome assessments via telephone using structured data collection tools at baseline, midpoint (~ 5 weeks), end-point (~ 10 weeks), and 6 months post-intervention. A subset of the participants from the trial will be invited for an in-depth, semi-structured interview, as discussed above (Aim 2), to better understand implementation and sustainability of behavior uptake.

All study-related data from the assessments will be entered into a UTSW REDCap database at: https://ais.swmed.edu/redcap/. Only de-identified data will be entered in REDCap. The health coach or a research staff member will obtain daily versus weekly step counts from study participants as appropriate depending on the session content and activity tracker assignment.

Outcome Measures

For aim 1 researchers will collect relevant demographic and clinical data either from patient EMR data abstraction or directly from the participant during a tele-delivered session. The research team will also collect various data points at specific intervals throughout the study duration using REDCap outcome assessment tools. A description of outcome assessment tools are included below. For aim 2, researchers will ascertain key barriers and facilitators to implementing MOTIVATE in a diverse older population in primary care and will explore factors critical to eventual uptake of MOTIVATE, e.g., acceptability, adoption, sustainability. The in-depth, semi-structured interviews will include a discussion guide with prompts focusing on acceptability, adoption, appropriateness, and sustainability of implementing MOTIVATE with older adults in primary care. All of these categories are relevant to patients, clinicians, and leadership, though nuances will emerge during interviews. We will stop conducting interviews once we reach thematic saturation and no further responses/ themes are provided.

Feasibility Outcomes

Feasibility outcomes, including recruitment and fidelity, will be collected and are intended to inform future grant proposals for a fully powered hybrid effectiveness/implementation award. All health coaching tele-sessions will be audio recorded using a telephone recording adapter (Model: LRX 40 USB) or audio recorders built into the telephones in DPDS. 20% of study sessions will be assessed using a fidelity checklist to ensure that the intervention is being delivered as intended. The fidelity checklists will be submitted along with this IRB. The purpose of the fidelity checklists is to verify that the objectives and core concepts for each session are being delivered as intended to the participants. Feasibility outcomes include, enrollment rates across GIM primary care and Parkland internal medicine/primary care clinic or community outpatient clinics, intervention adherence (measured as number of sessions the participant engaged in), and retention rate.

Primary outcomes for future effectiveness trial will be assessed:

- Physical function/ self-reported disability will be measured by the Roland Morris Disability Questionnaire (RMDQ). The RMDQ is valid, reliable and responsive to change in community dwelling patients with cLBP. Pain disability is important because this is a major treatment target in patients with chronic pain.
- Depression will be measured using the validated PHQ-9. A PHQ-9 cutoff score of >10 will signify clinically meaningful symptom burden (sensitivity and specificity =88% for major depressive disorder).

Secondary outcomes include physical, psychosocial consequences associated with cLBP and depression:

- Pain interference and pain behavior will be measured using NIH PROMIS instruments.
- Pain intensity will be measured with the PEG Three-Item Scale, which assesses average pain intensity, interference with enjoyment of life, and interference with general activity on a scale from 0 to 10).
- Quality of life will be measured with the well-validated PROMIS Global Health scale (physical and mental health).
- Social functioning is an important contributor to disability in those with depression and chronic pain. We will measure social isolation using PROMIS measures.
- Current medications (regularly scheduled and as-needed) will be collected at baseline and subsequent assessments from the EMR and then confirmed with the participant over the tele. Participants are also asked if they are taking additional medications. As described, we will create four "yes/no" variables reflecting medication use: acetaminophen, non-steroidal anti-inflammatory drugs (NSAIDs), opioids (including tramadol), and other agents such as anti-depressants used specifically for pain (versus depression), gabapentin, other anticonvulsants, corticosteroids, topical anesthetic and capsaicin preparations.
- Variables abstracted from the electronic medical record include (baseline, 3, 6): opioid use, psychotropic medications, hospitalizations, clinic visits (including mental health appointments), and unexpected clinic visits (included emergency department and/or urgent care clinics). These are important health utilization outcomes that will be explored in future studies.

Proximal/behavioral outcomes:

• Physical activity: We will evaluate overall physical activity level using a portable, lightweight, Omron HJ-320 pedometer. Participants will wear the pedometer clipped to their right lateral waistband for 24 hours per day for seven consecutive days (except during shower or water activities) to obtain five complete days of physical activity data. This will be explained in detail at the time of recruitment call. More details about the device and instructions for use are included for IRB review.

Other measures associated with achieving behavioral and clinical outcomes:

- Program satisfaction will be assessed during the end assessment. Including 1) To what extent has the study coach met your needs? 2) In an overall sense, how satisfied are you with the services that you have received with the MOTIVATE program? 3) If your friend or family member had pain and depression, would you recommend the MOTIVATE program to them? 4) Did the MOTIVATE program help motivate you to become active? 5) Did the MOTIVATE program help you understand the connection between pain, depression and activity? 6) Did the MOTIVATE program help you link goals to your values?
- Arthritis Self-efficacy scale is a 10 point Likert scale that measures the belief or confidence the participant has to perform 8 specific activities or tasks, based on arthritis.
- Physical activity contemplation ladder.
- Expectations of the intervention are asked with the following three questions: 1) How likely is this program to improve my ability to walk? 2) How likely is this program to improve my back pain? 3) How likely is this program to improve my depression/mood?
- Global impression of change will be assessed using the Patient Global Impression of Change Scale, a 7-point scale (1 = No change (or condition has gotten worse) to 7 = great deal better and a considerable improvement that has made all the difference) asking participants to rate their change (if any) in pain since starting the study.
- Pain Stages of Change Questionnaire (PSOCQ) evaluates attitudes, intentions, and behaviors consistent with stages of change for pain self-management.
- Therapeutic alliance will be assessed using the Working Alliance Inventory Short-Form will measure therapeutic relationship between patients and therapist (health coach in our study). To allow the therapeutic relationship to develop, participants will complete this assessment starting at 5 weeks.
- Sleep will be measured using the PROMIS Sleep SF 6-item.
- Resilience will be assessed using Connor Davidson Resilience Short Form: CDRISC 10 item.
- Claims/Billing and Healthcare Utilization: As part of the pilot study we are requesting claims billing
 data (from insurers) as well as administrative data from EMR or other UTSW or Parkland data
 sources to include the following data domains: all visits (outpatient, inpatient, ED visits, urgent care,
 physical therapy), procedures (in/outpatient; injections, surgery), imaging, and medications and
 their associated diagnosis/procedure codes (which our research team will use to determine if pain,
 degenerative joint disease, depression-related).

Table 2. Demographic and Clinic	al Data Poin		come Asses	sment Instr	ument	5
DATA	SOURCE	PRE- SCREEN	SCREEN	BASELINE	MID	END
Sex	EMR	Х		Х		
Age 50+	EMR	Х		Х		
ICD-10 back pain	EMR	Х				
ICD-10 depression	EMR	Х				
History of suicidal ideation	EMR	X				
Psychotic or suicidal hospitalization w/ past year	EMR	Х				
Telephone	EMR	Х				
	Phone					
Inclusion/Exclusion Criteria						
50 or older (confirm)	Phone		Χ			
(Clbp confirm) Low back pain (+/-radiation) on most days for the past 3 months?	Phone		Х			
(Clbp confirm) Does your back pain limit your ability to do activities around the home or activities that you enjoy?"	Phone		Х			
Rate pain level in past week (Scale 0-10)	Phone		Х	Х	Х	Х
Self-report hearing/visual challenges	Phone		Х			
Lumbar surgery within past year	Phone		Χ			
Recent illness/diagnosis of concern	Phone		Х			
Bed bound	Phone		Х			
Use of wheelchair around the house	Phone		Х			
Safety & Physical Activity	Phone		Х			
Cognitive Screener	Phone		Х			
Patient Health Questionnaire (PHQ-9)	Phone		Х	Х	Х	X
Self-Report Demographics and Other	Clinical Vari	ables				
Race/Ethnicity	EMR Phone			Х		
Education	EMR Phone			Х		
Marital Status	EMR Phone			Х		
Living situation	EMR Phone			Х		
Address	EMR Phone			Х		

Charleston Age Comorbidity	EMR	Х		
Calculator				
Body mass index	EMR	Х		
Medication list	EMR	Х		
	Phone			
Pain injections at ER/outpatient in	EMR	Х	Х	Х
the last month				
Med/mental/PT appointments	EMR	Х	Х	X
(related to Clbp/depression) or	Phone			
ED/urgent care visits within the last				
6 months				
Financial situation	Phone	Х		
Most frequented primary care clinic	Phone	Х		
location				
Short Michigan Alcoholism	Phone	Х		Χ
Screening Test (SMAST)				
Drug Use Questionnaire (DAST)	Phone	Х		
Expectation of Intervention	Phone	X		
Pain Screen Tool (PEG)	Phone	X	Х	Χ
Self-Efficacy Arthritis	Phone	X	Х	Х
Roland Disability Quest: Rating	Phone	Х	Х	X
Scale for Low Back Pain				
Pain Catastrophizing Scale (PCS-EN)	Phone	X	Х	Х
Fear Avoidance Beliefs	Phone	Х	Х	X
Questionnaire (FABQ)				
Physical Activity Contemplation	Phone	Х	Х	Х
Ladder				
Exercise Questionnaire	Phone	Х	Х	Χ
General Health Questions	Phone	X	Х	Х
Pain Stage of Change	Phone	Х	X	Χ
PROMIS 1.2 Global Mental Health	Phone	Х	X	Χ
PROMIS 1.2 Global Physical Health	Phone	Х	Х	X
PROMIS SF 1.1 Pain Behavior	Phone	Х	X	Χ
PROMIS SF 2.0 Social Isolation	Phone	Х	Х	Χ
PROMIS 2.0 Physical Function	Phone	Х	Х	Х
PROMIS Sleep 6-item	Phone	Х	Х	Х
Med List and Med/Mental/PT	Phone	Х	Х	Х
Appointments				
Future Time Perspective (Time	Phone	Х		Χ
Horizons?)				
Global Impression of Change	Phone		Х	Χ
Working Alliance Survey	Phone		Х	Χ
Connor Davidson Resilience Short	Phone	Х	Х	Χ
Form: CDRISC 10 item				
Patient Satisfaction Question	Phone			Χ

Semi-structured Interviews

Upon intervention completion, among a subset of the participants only, a member of the research team, not the health coach, will conduct face-to-face or telephone based, in-depth, semi-structured interviews prompting responses concerning helpfulness of skills taught, overall satisfaction, and motivation uptake as related to the information presented in the intervention. Semi-structured interviews with patients will occur over the phone, while clinician semi-structured interviews can occur over the telephone or at location convenient for the participant-most likely to occur on a UTSW or Parkland location. The interviews will also help identify barriers and facilitators to delivering a successful intervention. Interview topics will use the PARiHS framework previously outlined in Table 1.

Analysis

Feasibility outcomes will be measured by recruitment rates, adherence, retention, and intervention fidelity. We will add prompts during the semi-structured interviews that focus on how participants, if applicable, achieved an increase in physical activity. For example, did they build more walking-based activities in their daily routine (walking to the store rather than driving) or did they add new activities to accumulate more steps? We will also inquire about whether goals achieved were congruent with motivations to change behavior and how these motivations may influence sustained behavior. Fidelity assessment, as described above, will result in feedback to the health coaches and will ensure that the health coaches deliver the intervention as intended.

Analysis of the aim 2 qualitative data will be consistent with methods used in our prior research, using the constant comparative method. Interviews will be audio recorded and professionally transcribed. The qualitative data will be managed for coding and analysis of salient themes using NVIVO software, available to staff in [name] group. These results will inform procedural modifications and trial design decisions for a larger scale RCT to further evaluate MOTIVATE.

Proposed Analyses

Exact binomial method will be used to estimate rates of recruitment, intervention adherence, retention, and drop-out along with the corresponding 95% confidence intervals. Multiple levels of treatment retention will be defined, including partial intervention completion (% who do not complete all sessions), intervention dropout (% who dropout of intervention but continue to do assessments), research dropouts (% who remain in intervention, but do not complete assessments), and intervention + research dropouts (% who do not complete intervention or assessments). We will further break down the enrollment and retention calculations by examining enrollment/retention differences by treatment group, health coach, sex, age, race/ethnicity, and initial cLBP and depression severity using cross-classification tables.

As exploratory analyses, pre- and post-improvement in disability (RMDQ) and depression (PHQ-9) scores, as well as secondary and intermediate outcomes, from baseline to three months will be compared based on a two-sample t-test or Wilcoxon rank-sum tests between the two groups. The difference in improvement will be estimated and the 95% confidence interval will be reported. We will

estimate the preliminary effect size and variance of effect for the above outcomes. Linear mixed models will be used to assess whether there is a difference in the above outcomes over time within and between the two groups. We will include distance (in miles) from a UTSW or Parkland facility as a covariate in the exploratory outcome analyses, as suggested by reviewer.

We will describe, for the subset of participants receiving the intervention, whether physical activity (proximal outcome) and clinical outcomes (disability and depression scores) change over time based on the 1) proportion of the total sessions completed, and 2) the proportion of individual sessions completed. This will help us estimate optimal dose of the intervention (for example, whether completion of 4 vs. 7 vs. 8 of 10 sessions produces similar outcomes) and may inform which specific sessions are absolutely critical. SAS (version 9.3, Cary, NC) statistical software will be used.

Our formative evaluation may help to identify parts of the process that need refinement to maximize the feasibility and extension of the project to different sites in the future. Also part of the formative evaluation process will be to understand how implementation factors influence the optimal dose of our intervention. This evaluation may highlight which intervention components (or active ingredients) resulted in a change in behavior or other outcome result and potentially why (barriers/facilitators of change from an implementation standpoint).

Potential Risks

The risks to the study are minimal. The research involves a tele-delivered program by a health coach over 10-20 weeks followed by an interview; hence, there is minimal risk of physical injury. Participants will be asked to be more physically active and track their steps with a pedometer. As they become more active there is a risk of fall and injury. However, the health coach will focus on safely increasing walking and fall prevention strategies. The amount of activity we are asking participants to do is considered standard of practice and not strenuous activity that could result in injury. Another possible risk to patients is loss of time and potential breach of confidentiality. Risks include participant burden and resulting fatigue. There is no economic or legal risk in this study. To prevent or minimize any potential risks, patients may stop the interview at any point during this study if they feel any distress.

Discussing pain or psycho-social factors including comorbid depression may result in further psychological distress. There is no economic or legal risk in this study. To prevent or minimize any potential risks, the participant may stop the health coaching, assessments, or interview process at any time.

Since we will be recruiting older adults with comorbid depression, we have a plan in place should a participant be found to have worsening mental health conditions(s). If the participant develops worsening depressive symptoms during this study, the PCP will be notified to make appropriate follow-up or evaluation with Mental Health. In the case of suicidality endorsed, as standard measures at UTSW and Parkland, we will provide the suicide [contact]-TALK)) and a local 24/7 crisis [contact]), warm transfer to mental health specialist, follow-up with mental health services, and communication with the primary care physician. If the participant endorses suicidal or homicidal ideation during an in-person interview, the participant will be escorted to the Emergency Department

for in-person psychiatric evaluation. The PI will be immediately notified of any de-escalation of mental health conditions.

A protocol will be in place should the study team identify a potential participant who reports or develops suicidal ideation. For safety purposes, the protocol is as follows: any patient identified as having suicidal ideation during this screening process will be referred to [name], their respective Emergency Department, and referred to a national [contact]-TALK) or the local [contact]). Using a pre-established protocol, [name] will contact the participant and make arrangements for immediate mental health assessment and treatment based on the participant's symptoms. All suicidal patients will be provided with the suicide crisis hotline number, regardless of other immediate clinical interventions. Furthermore, participants with severe psychiatric diagnoses (as specified among the exclusion criteria) or prior documented inpatient admissions for suicidal ideation will be excluded and not enrolled in the study.

Procedures to Maintain Confidentiality

All electronic data will be stored within password protected data management programs, on password protected computers. All research staff will be trained in the appropriate safeguarding of confidential data and in the protection of human participants. At the end of the study, after analyses are complete, all study data will be de-identified, and the identifying key will be destroyed per UTSW policies and regulations.

All print information will be stored in locked files. The print information will be destroyed one year after the study completion date. Personally identifying data (name, address, and phone number) will be obtained from the UTSW and Parkland EMR system for the purpose of identifying potential participants and conducting calls in a secure password-protected database. Only members of the research team will have access to this information. All electronic information (survey database) will be stored on password-protected files on secure network servers. Identifiers will be destroyed after the study completion. Only IRB approved study personnel will have access to study data.

We anticipate that our procedures to minimize risk of confidentiality will be highly effective. In the unlikely event of loss of patient confidentiality, we will have a procedure in place for responding in timely and appropriate manner. The study participant who experiences loss of confidentiality will be informed by the Principal Investigator ([name]) in writing and by phone of the loss of confidentiality. UTSW and Parkland clinical leadership, the IRB, and participant will be informed in the case of such an occurrence.

Payment to Participants for Their Participation

For this study, we will provide incentives to all the participants who will be recruited (n=50). Each participant will receive a modest incentive after completion of each data collection assessment. Participants will be paid \$15 after completion of each outcomes assessment (this does not include the intervention health coaching sessions), and after completion of the in-depth interview, if selected. This will include assessments at baseline, mid-intervention at ~ five weeks, post intervention at ~10 weeks,

six-month interviews, and in-depth interview (only if selected) for a total of potentially \$60-75 if they complete all assessments of the study.

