In aim 1, we will assess the feasibility of a tele-delivered behavioral change intervention among older adults (aged 50 and older) with cLBP and depression. Fifty participants will be randomly assigned to one of two groups, behavioral intervention arm (n=25) versus the waitlist control arm (n=25). The active intervention will include eight tele-delivered health coach sessions and three tele-based outcome assessments. Each tele-based outcome assessment is roughly 45-60 minutes, and will be conducted by a member of the research team and will be recorded for research purposes. Each intervention session will be delivered by a trained health coach over a period of 10-20 weeks (up to 5 months total, accounting for additional time between sessions if needed). Aim 2 will involve one, in-depth, telephone-based, semi-structured interview at 6 months post-intervention. The health coach/research coordinator will identify participants who are at higher risk for drop-out, less engaged, or particularly successful at achieving behavioral change. The purpose of this interview is to learn about the barriers and facilitators to successful intervention delivery and integration within primary care, participant retention and acceptability from the clinician, patient, and health coach perspective. We will explore factors that are critical to eventual uptake of MOTIVATE; informed by Proctor's Framework of Implementation Outcomes we will focus on acceptability, adoption, appropriateness and sustainability of MOTIVATE. Semi-structured interviews with patients will be occur over the telephone, while clinician semistructured interviews can occur over the telephone or at a location convenient for the participant-most likely to occur on a UTSW or Parkland location.

The first session will introduce the participant to the health coach and the program, establish rapport, and measure baseline physical activity. The following six sessions address behavioral determinants, followed by a final session designed to be a booster session to the overall program.

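### Table 2 asks about visits over the last 6 months at about weeks 5 and 10, so most of each follow-up window precedes baseline, which adds noise and weakens relative comparisons

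*Combined protocol and SAP*

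**What the plan says.** One row of Table 2 covers medical, mental health and physical therapy appointments related to back pain or depression, or "ED/urgent care visits within the last" 6 months (the label runs on to the next line). Its sources are the EMR and the phone. It carries three marks. The column positions were lost in the extracted text, so I read them as baseline, MID and END, as for the PEG and Roland rows.

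Outcome Assessments and Data Collection sets the follow-up calls at "midpoint (~ 5 weeks), end-point (~ 10 weeks), and 6 months post-intervention". The payment section repeats "mid-intervention at ~ five weeks, post intervention at ~10 weeks". Study Design, however, has the sessions "delivered by a trained health coach over a period of 10-20 weeks (up to 5 months total", so an END call made after the last session could come later than week 10.

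Other places bear on the same data:

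- The secondary outcomes list says "Variables abstracted from the electronic medical record include (baseline, 3, 6", with no unit printed. It covers hospitalisations, clinic visits and emergency or urgent care visits, and adds: "These are important health utilization outcomes that will be explored in future studies".
- The list of other measures says "As part of the pilot study we are requesting claims billing" data, together with administrative data on all visits.
- A later Table 2 row, by phone only, covers the medication list and appointments at three assessments and states no look-back.
- Proposed Analyses says that improvement in the outcomes "from baseline to three months will be compared based on a two-sample t-test or Wilcoxon rank-sum tests", as an exploratory analysis, with effect sizes and linear mixed models to follow.

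**The concern.** A 6-month look-back suits baseline, where it describes prior use. Repeated 5 or 10 weeks later, it mostly asks again about time before the intervention began. Successive answers then share most of their visits, and only a small part of each can reflect allocation.

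At stake is the quality of the utilisation estimates that the pilot hands to the larger trial. A ratio or percentage comparison of such counts would look closer to no effect than it should. A standardised effect would be too small, because its denominator includes variation from visits that treatment could not have changed. Staff also cannot tell which window applies, since the EMR list, the first Table 2 row and the later phone row describe similar data differently.

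**Working it through.** The documents give no visit rate, expected effect or power figure for visits, so there is no stated number to reproduce.

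**Inputs from the documents:** look-back of 6 months, taken as 26 weeks; MID at week 5 and END at week 10; three months (week 13) from Proposed Analyses; week 20 as the latest end of delivery; 25 per arm.

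**Assumptions, not in the documents:** baseline coincides with the start of any effect; constant visit rate of 4 per 26 weeks (range 2 to 8); true rate ratio (RR) 0.70 after baseline; two-sided 5% level.

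**1. Share of the window before baseline** = (26 − t)/26.

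- Week 5: 21/26 = 81%
- Week 10: 16/26 = 62%
- Week 13: 13/26 = 50%
- Week 20: 6/26 = 23%
- Week 26: 0%

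**2. Overlap.** The baseline window runs from week −26 to 0, MID from −21 to 5, END from −16 to 10. MID and END share weeks −16 to 5, which is 21 of 26 weeks. All three share weeks −16 to 0.

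**3. Relative scale.** Apparent RR = 1 − (t/26)(1 − 0.70).

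- Week 5: 1 − 0.192 × 0.30 = 0.94
- Week 10: 1 − 0.385 × 0.30 = 0.88

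Only 19% and 38% of the relative reduction remain visible.

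**4. Absolute scale.** At week 10 the control arm expects 4 × 10/26 = 1.54 visits since baseline, and the difference is 1.54 × 0.30 = 0.46 visits. The 16 pre-baseline weeks add 4 × 16/26 = 2.46 expected visits to each arm, so the raw 6-month count also differs by 0.46. In the change score, END minus baseline equals visits in weeks 0 to 10 minus visits in weeks −26 to −16. The shared weeks cancel and the expected difference is again 0.46. A simulation with 200,000 per arm gave mean changes of 0.00 (control) and −0.46 (intervention).

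**5. Noise.** Standardised effect = 0.46 / √(mean of the two arm variances), Poisson counts, week 10:

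| Measure | Variance, control / intervention | Effect | Power, 25 per arm |
|---|---|---|---|
| Count since baseline | 1.54 / 1.08 | 0.40 | 30% |
| Raw 6-month count | 4.00 / 3.54 | 0.24 | 13% |
| Change in 6-month count | 3.08 / 2.62 | 0.27 | 16% |

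The effect is 41% smaller for the raw count and 32% smaller for the change score, at any Poisson rate. For 2 to 8 visits per 26 weeks, power is 17% to 52% for the count since baseline, 9% to 22% for the raw count and 10% to 28% for the change score.

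**6. Sensitivity to overdispersion.** With strong between-patient variation (gamma shape 1, 4 visits per 26 weeks), the simulated standard deviations, control / intervention, were 1.96 / 1.48 since baseline, 4.43 / 3.97 for the raw count and 1.75 / 1.68 for the change. The effects become 0.27, 0.11 and 0.27: the change score loses nothing, while the raw count loses more than under Poisson.

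**7. Schedules side by side.** The EMR list's first time point matches the Table 2 baseline column. Its 3 and 6, if months, match no Table 2 column, although they fit the three-month comparison and the six-month follow-up. The 6-month assessment has no column in Table 2 either.

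**The case against.** The strongest reply is that the planned comparison is of change from baseline, where shared visits cancel and the expected difference keeps its size. That stands. A reader might infer from the window shares that any treatment effect is diluted; steps 4 and 5 show that only relative and standardised effects are, and the plan specifies no ratio analysis of visits. Cancellation does require the same old visits to be recorded identically at both calls, which is uncertain where the source is telephone recall.

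Second, no section names this row as an analysed outcome. The utilisation listed among the secondary outcomes is the EMR abstraction, which is deferred to future work, and nothing in the plan adds MID and END counts together. That also stands: one visit can appear at two or three assessments, but no planned estimate is shown to be corrupted by it.

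Third, a reader might infer that the counts can never be re-cut by date. The documents do not support this. The row draws on the EMR as well as the phone, claims data are requested, and the data form is not shown. Equally, no section says that visit dates are kept or defines a post-baseline window, so these sources are a possible remedy and not a stated one.

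Fourth, the 6-month wording follows the emergency and urgent care visits and may not govern the appointments. That is a fair reading, and a further reason to state the window.

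Finally, if END falls later than week 10, the problem there shrinks. MID stays at 81% if it is held at week 5.

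**Conclusion.** The point holds as a cheap improvement of minor severity. Followed as written, the row gives overlapping counts that are mostly pre-baseline at week 5 (81%) and at week 10 (62%), falling to 50% or 23% if END is at three months or week 20. The absolute difference between arms is not biased. The cost is a relative effect pulled toward none (RR 0.70 seen as 0.94 and 0.88) and a noisier comparison (standardised effect 0.40 reduced to 0.24 or 0.27 at week 10). Those figures rest on an assumed visit rate, RR and Poisson variation; with strong overdispersion the change-score loss disappears and the raw-count loss grows.

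The timing mismatch is real but partial: a reader might infer that the EMR schedule fits nothing in Table 2, yet it matches baseline. Nothing here threatens the feasibility aim. Utilisation is exploratory, and with 25 per arm power would be low even with a clean window.

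**What to change.** Keep the 6-month look-back at baseline only. At MID, END and the 6-month assessment, ask about visits since the previous completed assessment, and record that date so a missed call leaves no gap. Cut EMR and claims counts by visit date from randomisation, in both arms. Make the secondary outcomes list, the Table 2 visit row and the phone appointments row state the same windows, print the unit for 3 and 6, say which visit types each window governs, and add the 6-month assessment to Table 2.

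The cost is rewording two table rows, the phone script and one EMR query, with no extra calls. The drawback is that baseline and follow-up windows then differ in length, so simple change in count no longer applies. Compare counts as rates per unit of time, or compare follow-up counts with the baseline 6-month count as a covariate.
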